## **6. INVESTIGATIONAL PRODUCT INFORMATION**

### **6.1 ZX008 (FENFLURAMINE HYDROCHLORIDE ORAL SOLUTION)**

Sub-study subjects will receive ZX008 as part of their treatment in main Study ZX008-1503. A brief description of the ZX008 product is provided in Table 2.

**Table 2: Investigational Medicinal Product – ZX008**

	Study Product
Substance Code	ZX008
Active Substance (INN)	Fenfluramine Hydrochloride
Trade Name	Not applicable
Formulation (including dosage form and strength)	Solution 2.5 mg/mL
Route/Mode of Administration	Oral
Manufacturer	PCI Pharma Services on behalf of Zogenix International Limited

ZX008 is supplied as an oral solution in a concentration of 2.5 mg/mL. Subjects will be titrated to an effective dose beginning with 0.2 mg/kg/day (maximum: 30 mg/day). Study medication will be administered twice a day (BID) in equally divided doses with food. Please refer to the ZX008-1503 protocol for a detailed description of the ZX008 drug product and its administration.

## 6.2 EMPATICA EMBRACE SYSTEM

### 6.2.1 Hardware

[figure not shown]
The Embrace wrist-worn monitoring device (Embrace watch; Figure 1) reads physiological data from the surface of the skin and can transmit it wirelessly to a receiver. More specifically the electronic device measures: EDA, skin temperature, and motion (3-axis acceleration and 3D orientation with a gyroscope). Designed to be non-stigmatising for patients, the device also displays time in an analog-like display. User interactions are via a 12- full-color light-emitting diode (LED) circular display, vibration motor for haptic feedback and capacitive touch button.

**Figure 1: Embrace Wrist-worn Monitoring Device (Embrace Watch)**

## 6.2.2 Software

Figure 2: Embrace System Architecture

### 6.2.2.1 Embrace Alert App

The Embrace Alert app detects events from user physiology, such as a convulsive seizure, and sends an alert to a caregiver through a phone call or text message. Real-time seizure detection and alerting is still experimental and is for investigational use only. It also collects raw data from Embrace hardware and sends it to a receiver (smart phone memory) and consequently to a cloud storage system for later retrieval. The Alert app runs on an iPod Touch and must remain in close proximity of the patient. The Alert app is also used for device configuration (eg, setting the clock and activating/deactivating night-mode which suppresses interactions) and firmware management.

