**Study Product, Dose, and Mode of Administration:**

ZX008: supplied as an oral solution in a concentration of 2.5 mg/mL. Subjects will be titrated to an effective dose beginning with 0.2 mg/kg/day (maximum: 30 mg/day). Study medication will be administered twice a day (BID) in equally divided doses with food.

Empatica Embrace watch system (Embrace)/Embrace Alert app: The noninvasive Embrace wrist-worn monitoring device, reads physiological data (EDA, skin temperature, and motion) from the surface of the skin and can transmit it wirelessly to a receiver. The watch is used in conjunction with the Embrace Alert app. The Alert app detects events from user physiology, such as convulsive seizures, and sends an alert to a caregiver via a phone call or text message. The Alert app runs on an iPod Touch and must remain in close proximity of the patient.

**Duration of Treatment:** Subjects will be permitted to participate in the sub-study for the initial 12 weeks of participation in the main OLE study (ZX008-1503). Subjects may have the opportunity to extend participation in the sub-study for up to 24 weeks.

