### 1.2 RATIONALE FOR CURRENT SUB-STUDY, ZX008-1503-SS01

This is a sub-study to the ZX008-1503 OLE trial, which will include up to 20 participants who are enrolled in Study ZX008-1503. This is an exploratory sub-study to provide preliminary information on the overall usability and performance of the Empatica Embrace watch system (Embrace) in outpatients with Dravet syndrome.

Seizure frequency is the primary outcome measure for individual treatment and for clinical trials. The current gold standard for demonstrating efficacy of new anti-epileptic drugs is a 50% reduction in seizure frequency. This efficacy standard is based on patients or their caregivers maintaining seizure diaries.

Use of sensitive seizure detection technology may allow greater accuracy in seizure counting. Seizure detection technology may also provide means to address specific clinical questions, such as the occurrence of unwitnessed seizures during periods of sleep.

The Embrace has been designed for automated convulsive seizure detection and characterization. The Embrace watch monitors electrodermal activity (EDA) and accelerometer-sensed changes in motion to analyze the information and detect patterns that are typically observed in convulsive seizures in real-time. The data can then be used to compare seizure detections, false alarms, and seizures that are not detected, to e-diary seizure report information.

This sub-study for patients enrolled in the open-label extension study may provide insights into seizure triggers, such as temperature, or facilitate seizure counts during sleep and allow for comparison of various endpoints captured by the Embrace to the same endpoints captured in an electronic hand-held seizure diary.

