### 3. INVESTIGATIONAL PLAN

#### 3.1 OVERALL STUDY DESIGN AND PLAN

This is a sub-study to the ZX008-1503 OLE study. All participants in this sub-study will have participated in Study ZX008-1501 or ZX008-1504 Cohort 2 in the United States or Canada and then continued in Study ZX008-1503, which is a multicenter, open-label, long-term safety study of ZX008 (fenfluramine hydrochloride) in pediatric and young adult subjects with Dravet syndrome. The main Study ZX008-1503 consists of a 12-month OLE Treatment Period and a 2-week Post-Dosing Period in which all subjects will receive ZX008 starting at 0.2 mg/kg, titrating to an effective dose, up to 0.8 mg/kg/day (not to exceed 30 mg/day). Thus, subjects who complete the main study will have been treated with ZX008 for a minimum of up to 1 year. This sub-study will include up to 20 participants who meet the entry criteria for the main Study ZX008-1503 and who are willing to wear the Embrace watch and their parent/caregiver who is willing to use the Embrace Alert app per the user instructions for 12 consecutive weeks. Those invited to participate will undergo all procedures included in the main Study ZX008-1503, plus any additional procedures for the sub-study. At the conclusion of the sub-study, participants will only use the ERT seizure diary for the remainder of their participation in the main Study ZX008-1503. Efficacy analyses for sub-study participants that rely on the ERT seizure diary or that are specific to the Embrace watch will not be included in the main ZX008-1503 analyses.

At the time of consent for the main Study ZX008-1503 subjects will also be presented with the consent for this sub-study. Subjects who consent to participate in the sub-study will be fitted with an Embrace watch at Study Visit 1. Subjects (and/or parents/caregivers) will also be given instructions on how to use the Embrace system. The Alert app must be running on the provided iPod touch and remain in close proximity of the patient. However, parents/caregivers will continue to use the ERT seizure diary to record the number/type of seizures, use of rescue medication, and study drug administration.

At pre-determined assessment times, parents/caregivers will complete questionnaires specific for the sub-study, including:

1. Ease of Use Questionnaire, which comprises a 5-point Likert scale (1- Very easy, to 5- Very difficult).
2. Perceived Stress Scale (PSS), which consists of 10 items.

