### **4.1 INCLUSION CRITERIA**

In addition to meeting all of the main Study ZX008-1503 inclusion criteria subjects in the sub-study must also be willing to wear and use the Embrace watch and parents/caregivers must be willing to use the Alert app. This includes:

1. Subject is willing to wear the Embrace watch on the wrist (alternatively ankle, if needed for younger children). Subjects are asked to wear the watch for as many hours of the day as possible and for the entire night, if possible, for the duration of the sub-study.
2. Subject's parent/caregiver is willing to use the Alert App and receive voice and SMS notifications on their personal smart-phone, and ensure the smart-phone has internet connectivity; iOS 8.2 or higher is required for iPhone users.
3. Subject/subject's caregiver is willing to ensure that the Embrace watch remains within close proximity of the paired iPod Touch running the Empatica Alert app.
4. Subject/subject's caregiver is willing to ensure that the Embrace system is properly stored when not in use, and is not left exposed to direct sunlight, moisture, humidity or rain while in storage. The Embrace watch is water resistant but should never be submerged in water. Bathing and/or showering with the watch is acceptable, however.
5. Subject/subject's caregiver is willing to regularly clean the Embrace watch, routinely inspect the watch for sharp edges and damage, and ensure the watch is never worn over damaged or broken skin.
6. Subject/subject's caregiver is willing to ensure that the Embrace system is properly charged daily during a time when the subject is being observed so any seizures that occur during times that the device is not being worn are able to be added to the record manually.

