## **5. STUDY VISITS AND PROCEDURES**

Subjects participating in the sub-study will undergo all clinic visits and procedures included in the main Study ZX008-1503, plus additional procedures for the sub-study, as described in Table 1. The following questionnaires/scales will be completed at the specified time points:

- To assess user experience with the Embrace watch system, a 5-point Likert Ease of Use Questionnaire ([Appendix 1](#)) will be completed at Clinic Visit 2 (Day 15), monthly at Clinic Visits 3-7, and at the end of study participation (Clinic Visit 8).
- The Perceived Stress Scale (PSS) ([Appendix 2](#)) is the most widely used psychological instrument for measuring the perception of stress. It is a measure of the degree to which situations in one's life are appraised as stressful. It is a 10-item scale that asks about feelings and thoughts during the last month. In each case, respondents are asked how often they felt a certain way. The PSS will be used to evaluate whether objective seizure detection and automated seizure alerts have any impact on perceived stress of the parent/caregiver. This scale will be completed at Clinic Visit 1 (Day 1), monthly at Clinic Visits 3-7, and at the end of study participation (Clinic Visit 8).
- The EQ-5D-5L (see main Study ZX008-1503) is a standardized measure of health status used to provide a simple, generic assessment for clinical and economic appraisal. It consists of 6 questions and can be completed in less than 10 minutes. The EQ-5D-5L is included in the main study ZX008-1503, but for the sub-study the assessment should be as it relates to use of the Embrace watch. This questionnaire will be completed at Clinic Visit 1 (Day 1), monthly at Clinic Visits 3-7, and at the end of study participation (Clinic Visit 8).
- The Hospital Anxiety and Depression Scale (HADS) (see main Study ZX008-1503) is a tool commonly used to determine the levels of anxiety and depression that a person is experiencing. It is a 14-item scale that generates ordinal data. Seven of the items relate to anxiety and 7 relate to depression. The HADS is included in the main study ZX008-1503, but for the sub-study the assessment should be as it relates to use of the Embrace watch. This scale will be completed at Clinic Visit 1 (Day 1) monthly at Clinic Visits 3-7, and at the end of study participation (Clinic Visit 8).

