### 6.2.3 Usability of the Empatica Embrace Watch System (Embrace)

In the context of investigational use, the experimental seizure detection and alert components can be activated for patients and caregivers with their informed consent about the experimental nature of the functionality. Usability testing to support patient home-use has been underway since March 2016 with eight iterations introduced prior to August 2016 (revision history on hand as per the Embrace Change-log). In-app getting started guides, quick-start documentation and troubleshooting guides are sufficient to support the vast majority of patient caregiver groups in current trials. Due to the fact that patients/caregivers will be enrolled by study staff, those who might otherwise be unable to get set-up independently should be able to be enrolled and on-boarded without issue. The Empatica Alert app Onboarding screens are shown in Figure 3, and also provided in [Appendix 3](#).

Figure 3: Empatica Alert App Onboarding Screens

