#### **8.4 STATISTICAL METHODS**

All safety data will be summarized as described in the main Study ZX008-1503 protocol and associated Statistical Analysis Plan. Efficacy analyses for sub-study participants that rely on the ERT seizure diary or are specific to the Embrace will not be included in the main Study ZX008-1503 analyses. Exploratory data for the Embrace watch system data will be processed as follows:

Continuous data will be summarized using descriptive statistics including means, standard deviations, medians, lower and upper quartiles, and ranges. Categorical variables will be summarized with frequencies and percentages. Confidence intervals will be calculated for key parameters or estimates as warranted.

A complete description of the statistical analyses and methods will be available in the Statistical Analysis Plan, which will be finalized before the database is locked.

The primary analysis will rely on descriptive statistics to summarize responses to the Ease of Use Questionnaire from each time point where the questionnaire is administered. In particular, the modal, ie, most frequent, response to each item on the questionnaire will be reported at each time point. Responses across all items on the questionnaire will be summed to create an overall index that will also be reported at each time point.

Exploratory data for the Embrace watch system data will be processed as follows:

- Embrace’s automated convulsive seizure detection results will be manually compared to the diary counts of convulsive seizures. Spearman rank correlation will be used to quantify agreement.
- The Spearman rank correlation described above will be repeated separately for events during periods of sleep and for events while awake, based on Embrace’s determination of sleep/wake (periods of sleep will be based on actigraphy and EDA as measured by the Embrace watch).

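### Seizure alerts go to the caregivers who keep the diary, so the planned comparison measures alert-assisted agreement, not agreement with an independent diary

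*Combined protocol and SAP*

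**What the plan says.** - **Who is alerted.** Section 6.2.2.1 says the app "sends an alert to a caregiver through a phone call or text message", and the synopsis (Study Product) says the same. Under Section 4.1 a subject qualifies only if the "parent/caregiver is willing to use the Alert App and receive voice and SMS notifications on their personal smart-phone".
- **Who keeps the diary.** Section 3.1: "parents/caregivers will continue to use the ERT seizure diary to record the number/type of seizures".
- **Whether alerts are live.** Section 6.2.3 says that "the experimental seizure detection and alert components can be activated for patients and caregivers with their informed consent". Section 5 uses the Perceived Stress Scale to "evaluate whether objective seizure detection and automated seizure alerts have any impact on perceived stress of the parent/caregiver", which presupposes working alerts. No alert-off period is described.
- **How the two are compared.** Section 8.4: "Spearman rank correlation will be used to quantify agreement", repeated for sleep and for waking. The synopsis names Cohen's kappa for the same comparison. Section 2.2 adds a comparison of event timing.
- **Why it is compared.** Section 1.2 says detection technology may help with specific questions, "such as the occurrence of unwitnessed seizures during periods of sleep", and foresees setting detections, false alarms and missed seizures against the diary.

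Nothing masks the diary keeper to alerts, marks entries that followed an alert, or names an independent reference for a true seizure. The dependence is not mentioned.

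**The concern.** The comparison treats watch and diary as two separate measurements. With alerts on, a seizure the caregiver would have missed can enter the diary because the watch reported it. A false alarm that is entered also becomes a match.

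High agreement in sleep could then mean that caregivers miss little, or that the watch woke them. The planned output cannot separate these. A reader could take it as evidence that the diary is complete, or that the watch is sensitive, when it shows neither. The timing comparison is exposed in the same way, because a prompted entry may take its time from the alert.

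**Working it through.** The documents give no expected agreement, watch sensitivity, false-alarm rate or witnessing rate, so there is no figure of the plan's to reproduce. The direction can be reasoned out; every size below rests on assumed inputs.

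**1. Direction, event level.** Cross-classify time epochs as both, watch-only, diary-only or neither. A prompted entry arises only where the watch fired, so, if linked to its detection, it moves an epoch from watch-only to both. Let p_o be observed agreement, p_e chance agreement, p_W the share of epochs the watch flags, and d the share moved.

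- p_o rises by d.
- p_e changes by d(2p_W − 1), which is negative when the watch flags fewer than half of the epochs.
- 1 − kappa = (1 − p_o)/(1 − p_e). The numerator falls and the denominator rises, so kappa rises.

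**2. Event-level illustration.** Assume watch sensitivity s = 0.8, prompted-entry rate a = 0.9 for detected but unwitnessed seizures, witnessed share w, and no false alarms.

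- P(diary | watch) = w + (1 − w)a. Without alerts it is w.
- P(watch | diary) = s[w + (1 − w)a] / {s[w + (1 − w)a] + (1 − s)w}. Without alerts it is s.

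| w | P(diary given watch) | without alerts | P(watch given diary) | without alerts |
|---|---|---|---|---|
| 0.2 | 0.2 + 0.8 × 0.9 = 92% | 20% | 0.736/0.776 = 95% | 80% |
| 0.6 | 0.6 + 0.4 × 0.9 = 96% | 60% | 0.768/0.888 = 86% | 80% |

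Section 8.4 plans neither quantity. They show the mechanism only.

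**3. The planned statistics, similar response across families.** Simulation: 20 subjects, one 28-day period, mean 15 convulsive seizures (40% asleep), sensitivity 0.5 to 0.9, unprompted capture 0.90 to 0.95 awake and 0.3 to 0.7 asleep, false alarms 0.02 or 0.2 per day, prompted-entry rate 0.5 or 0.9. With no false alarms entered:

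| | Awake | Asleep |
|---|---|---|
| Rise in Spearman | 0.00 to 0.03 | 0.03 to 0.30 |
| Rise in hourly kappa | about 0.01 to 0.06 | 0.07 to 0.49 |

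One case (sensitivity 0.9, 0.02 false alarms/day, between-subject SD of sensitivity and capture 0.2, prompted-entry rate 0.9): awake with capture 0.95, Spearman went from 0.92 to 0.95; asleep with capture 0.5, from 0.77 to 0.93. If half of 0.2 false alarms per day are also entered (sensitivity 0.9), Spearman went from 0.69 to 0.91 awake (capture 0.90) and from 0.51 to 0.90 asleep (capture 0.5).

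**4. Spearman, uneven response.** Spearman uses ranks across subjects, so uneven response can scramble it. Simulation: 20 subjects, sensitivity 0.8, 0.5 false alarms per period (none entered), gamma-Poisson counts (shape 4), the same witnessed share for all. Half the families enter 90% of alerted missed seizures and half enter none.

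- Mean 15 seizures, 20% witnessed: 0.67 falls to 0.53. With uniform 90% response it rises to 0.96.
- Mean 40, 30% witnessed: 0.86 falls to about 0.65.

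When the witnessed share also varied between families, Spearman rose in every setting tried.

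**The case against.** **Importance.** This is a secondary exploratory comparison in a feasibility-sized pilot of up to 20 subjects, with usability as the primary objective, no decision rule, and full methods deferred to a later SAP. That stands. It limits the consequence but does not remove the dependence.

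**Direction.** A reader might infer that the Section 8.4 correlation is always overstated and hence an upper bound. Step 4 shows that this can fail. The upper-bound statement holds for event-level matching only.

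**Sleep.** A reader might infer that the bias is established as worst in sleep. That needs lower unprompted capture at night, which Section 1.2 makes plausible, and alerts that reach the caregiver at night. Section 6.2.2.1 describes a night-mode that suppresses interactions without saying whether caregiver alerts are included. If they are, the sleep effect shrinks.

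**Same person.** The overlap holds by role. The documents do not say that one person does both in every family, although an alerted person may well inform the diary keeper.

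**A lower bound.** It is tempting to bracket agreement by discarding every alert-preceded entry. Nearly every matched event has an alert, including those the caregiver saw, so this bound is near zero by construction. In the w = 0.6 example, 0.6/0.96 = 62.5% of the discarded matches were witnessed independently.

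**Linkage.** An alert follows onset, so a prompted entry that gives the onset time would appear to precede it. Seizure time cannot show prompting; entry time is needed. No section names an alert log or a diary-entry timestamp, and the diary's fields are in the main protocol, which is not available here.

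**Conclusion.** The concern holds in a limited form. The diary is not independent of the watch, and the plan makes no allowance for this. Event-level agreement is inflated relative to an unaided diary, given that prompted entries are linked to their detections. The Spearman correlation is usually inflated as well, but can fall when families differ strongly in how they act on alerts. The effect is probably larger in sleep if caregiver alerts are active at night.

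The size cannot be derived from the documents: awake it may be close to nil, and asleep it may be large. Prompted entries of true seizures do make the diary more complete, but the comparison then cannot show what an unaided diary would miss. The ease-of-use endpoint is unaffected.

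**What to change.** Keep the alerts. In Section 8.4, and in the SAP before database lock:

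1. Report event-level matching (both, watch-only, diary-only) with a stated matching window, overall and by sleep/wake, alongside the Spearman correlation.
2. Label the results as alert-assisted agreement. State that event-level agreement is an upper bound on agreement with an unprompted diary, and do not extend that wording to Spearman.
3. State that the results will not be interpreted as unaided diary completeness or as device sensitivity.
4. If alert-sent times and diary-entry times prove to be available, show matched events by whether the entry was made before or after the alert, as a descriptive sensitivity analysis. Do not report a bound that counts no alert-preceded entries.
5. State whether night-mode suppresses caregiver alerts, so that the sleep result can be read correctly.

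The cost is SAP text and some extra programming, plus a check of which timestamps exist. The downside is a more limited conclusion.
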